### **7.2 Selection of Doses in the Study**

The combined safety, pharmacokinetic, and efficacy data from CR845-CLIN2101 provided the basis for the selection of the dose and dose regimen of CR845 to be used in this study. The lowest dose tested (0.5 mcg/kg IV) appeared to be well tolerated and effective at reducing itch intensity over a period of 8 weeks.

### **7.3 Appropriateness of Measurements**

Standard clinical, laboratory, and statistical procedures and methodology will be utilized in this study. The PRO assessments to be used in this study are appropriate.

---

## 8.0 Statistical Methods

### 8.1 General Considerations

This section describes the statistical analysis of efficacy and safety data collected during the Double-blind Phase only. The analysis of safety and efficacy data collected during the Open-label Extension Phase will be included in the SAP.

The SAP will provide a detailed description for the handling of missing data, patient eligibility criteria for the analysis, and statistical methodology. If differences occur between analyses of double-blind data described in the SAP and the current protocol, those found in the SAP will assume primacy. In addition, the SAP will provide details for the analysis of data collected during the Open-label Extension Phase, including the analysis of safety data during exposure to CR845 across both the Double-blind and the Open-label Extension Phases.

Unless otherwise noted, continuous variables will be summarized using number of non-missing observations, mean, standard deviation, median, minimum, and maximum; categorical variables will be summarized using the frequency count and the percentage of patients in each category. In addition to the descriptive summaries, pertinent data listings will be provided.

All analyses will be performed using SAS® version 9.2 or higher, unless otherwise specified.

### 8.2 Determination of Sample Size

The planned sample size for this study is 350 (175 per treatment group) male and female hemodialysis patients with chronic moderate-to-severe pruritus (mean baseline 24-hour Worst Itching Intensity NRS score  $\geq 5$ ), randomized at approximately 95 clinical sites. The sample size may be increased to 500 patients (250 per treatment group) based on the results of a planned unblinded interim assessment conducted when approximately 50% of the planned 350 first patients have been randomized and have either completed the 12-week Double-blind Treatment Period or have discontinued from double-blind treatment early. The planned interim assessment will be conducted by an Independent Data Monitoring Committee (IDMC). Details related to the sample size re-estimation are included in [Section 8.4.1](#).

The sample size calculation is based on results of a completed Phase 2 double-blind, placebo-controlled study (CR845-CLIN2101) of CR845 in hemodialysis patients who had moderate-to-severe pruritus. In this study, approximately 30% of patients randomized to the placebo group reported  $\geq 3$ -point improvement from baseline with respect to the 24-hour Worst Itching Intensity NRS at the end of treatment (Week 8). The proportion of patients who received CR845 and reported a similar improvement in itch scores ranged from approximately 60% to 45% (ie, 30% to 15% difference from

placebo), depending on the dose of active study drug (0.5 mcg/kg, 1.0 mcg/kg, 1.5 mcg/kg).

Given a sample size of 350 patients (175 per treatment group) and assuming a true response rate of 30% for the placebo group and a true response rate of 50% for the CR845 group (defining response as an improvement from baseline  $\geq 3$  points with respect to the Worst Itching Intensity NRS at Week 12), a 2-sided continuity corrected Chi-square will have 96% power to detect a treatment difference. The power of this test statistic would be  $\geq 84\%$  for differences from placebo as low as 0.16 (Table 4).

**Table 4. Power as a Function of Effect Size (N = 175 per arm)**

Placebo Response	0.30	0.30	0.30	0.30
CR845 Response	0.50	0.48	0.46	0.45
Odds Ratio	2.333	2.154	1.988	1.909
Powera	96%	92%	84%	79%

a. Power for a 2-sided Chi-square continuity-corrected test and a 5% Type 1 error.

Based on results of a planned interim assessment, the sample size may be increased up to 500 patients (250 per treatment group). Given this maximum sample size, and assuming a true response rate of 30% in the placebo group, a 2-sided continuity corrected Chi-square would have approximately 90% power to detect a treatment difference when the CR845 response rate is 45% (a 15% difference from placebo) (Table 5).

**Table 5. Sample Size as a Function of Odds Ratio (90% Power)**

Placebo Response	0.30	0.30	0.30	0.30	0.30
CR845 Response	0.50	0.48	0.46	0.45	0.44
Odds Ratio	2.333	2.154	1.988	1.909	1.833
Sample Sizea	134	164	204	230	262

a. Sample size for a 2-sided Chi-square continuity-corrected test and a 5% Type 1 error.

### 8.3 Randomization

Before the start of the study, a computer-generated randomization schedule will be prepared. Randomization will be performed using an IVRS/IWRS. Patients will be randomized in a 1:1 ratio to receive either CR845 0.5 mcg/kg IV or matching placebo IV during the Double-blind Treatment Period. Patients will be stratified according to their use or non-use of concomitant medications to treat their itch during the week prior to randomization (Run-in Period) as well as the presence or absence of specific medical conditions. These medical conditions include:

- History of fall or fracture (related to fall)
- Confusional state or mental status change or altered mental status or disorientation
- Gait disturbance or movement disorder

All eligible patients will receive CR845 at a dose of 0.5 mcg/kg starting on Day 1 of the Open-label Extension Phase.

## **8.4 Interim Analysis**

### **8.4.1 Sample Size Re-estimation**

An unblinded interim analysis for sample size re-estimation will be conducted when approximately 50% of the first 350 patients have been randomized and have either completed the 12-week Double-blind Treatment Period or have discontinued from double-blind treatment early. The planned interim assessment will be conducted by an IDMC. An unblinded statistician who will not be part of the study team will provide results of the interim analysis to the IDMC members. Members of the IDMC will not participate in the Data Safety Monitoring Board (DSMB) and will not be members of the study team. During the interim assessment, the study team will remain blinded to the data; however, the IDMC will receive unblinded summary results to implement the decision rule for sample size re-estimation. The IDMC will only communicate the decision to either keep the original sample size or to increase it; no other results will be provided to blinded staff. The DSMB will be made aware of the decision, but not given the results that were the basis of the decision.

[REDACTED]

[REDACTED]

[REDACTED]

[REDACTED]

[REDACTED]

[REDACTED]

[REDACTED]

[REDACTED]

#### **8.4.2 Safety Data Review**

Safety data will be reviewed on an ongoing basis by the Sponsor and a DSMB. The operation of the DSMB will be governed by a charter that will describe the meeting frequency, procedures, and requirements for reporting its observations to the Sponsor.

#### **8.5 Analysis Populations**

The Enrolled Population is defined as the group of patients who sign informed consent.

The ITT Population is defined as the group of patients who are randomized to a treatment group.

The Double-blind Safety Population is defined as the group of randomized patients who received at least 1 dose of double-blind study drug during the Double-blind Treatment Period.

Following the intent-to-treat principle, patients in the ITT Population will be analyzed according to their randomized treatment, regardless of the actual treatment received. Patients in the Double-blind Safety Population will be analyzed according to the actual treatment received. The Double-blind Safety Population will be used to analyze all safety endpoints collected during the Double-blind Phase, while the ITT Population will be used to analyze all efficacy endpoints collected during the Double-blind Phase.

The Per-Protocol Population is defined as the subset of patients in the ITT Population who do not have any major protocol deviations that could affect the efficacy analyses of the double-blind data. An analysis of the primary and secondary efficacy variables for the Per-Protocol Population will be performed.

Key exclusions from the Per-Protocol population include patients who:

- Received less than 80% of the planned study drug doses
- Had a mean baseline Worst Itching Intensity score < 5.0
- Had a missing average 24-hour weekly Worst Itching NRS score for  $\geq 25\%$  of study weeks
- Had significant amounts of restricted and prohibited medications ([Section 6.4.9](#)) based on medical review
- Received a different treatment than the treatment to which they were randomized

Inclusion in the Per-Protocol Population will be determined prior to unblinding the data.

---

The Open-label Safety Population is defined as the group of patients who receive at least 1 dose of study drug in the Open-label Extension Phase. The Open-label Safety Population will be used to analyze all safety endpoints collected during the Open-label Extension Phase, and during exposure to CR845 combining data from both the Double-blind and the Open-label Extension Phases.

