### **6.1.2 Open-label Extension Phase**

Patients who received at least 30 doses of study drug (either placebo or active) during the 12-week Double-blind Treatment Period and continue to meet other eligibility criteria will be eligible to receive open-label CR845 for an additional 52 weeks. The Open-label Extension Phase will be comprised of the Open-label Treatment Period and the Follow-up Period. The first visit and first dosing for the Open-label Extension Phase of the study will occur immediately on the day of the last visit of the Double-blind Treatment Period or up to 1 week following the Double-blind Treatment Period. Each patient will receive CR845 at a dose of 0.5 mcg/kg after each dialysis session, 3 times per week for up to 52 weeks, whether they had been previously administered placebo or CR845. Prescription dry body weight will be recorded at the start of and every 12 weeks during the Open-label Extension Phase; if there is a  $\pm 10\%$  or more change from the prescription dry body weight recorded at Screening, then the CR845 dose will be adjusted according to the newly recorded dry body weight.

Patients will complete the 5-D Itch Scale during Weeks 4, 8, 12, 24, 36, and 52 (preferably at the end of the specified weeks).

Clinical laboratory tests, vital signs, adverse events, and concomitant medications will be monitored throughout the Open-label Treatment Period. Blood samples for inflammatory biomarkers will be collected periodically until the End-of-Treatment or Early Termination Visit. An electrocardiogram will be performed at the End-of-Treatment or Early Termination Visit.

The number and reason(s) for missed dialysis and the use of antipruritic medications will be recorded throughout the Open-label Extension Phase.

The last dose of open-label study drug will be administered at the last dialysis visit in Week 52.

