  9. Has at least 2 single-pool Kt/V measurements  $\geq 1.2$ , or at least 2 urea reduction ratio measurements  $\geq 65\%$ , or 1 single-pool Kt/V measurement  $\geq 1.2$  and 1 urea reduction ratio measurement  $\geq 65\%$  on different dialysis days during the 3 months period prior to screening;
  10. Prior to randomization:
    - a. Has completed at least four out of eight Worst Itching Intensity Numeral Rating Scale (NRS) worksheets from the start of the 7-day Run-in Period up to and including the pre-randomization assessment on Day 1;
    - b. Has a mean baseline Worst Itching Intensity NRS score  $\geq 5$ , defined as the average of all non-missing scores reported from the start of the 7-day Run-in Period up to and including the pre-randomization assessment on Day 1.

**To be eligible for inclusion into the Open-label Extension Phase of the study, each patient will have to fulfill the additional following criteria at the time of entry into the Open-label Extension Phase:**

11. Has received at least 30 doses of the planned 36 doses of study drug during the Double-blind Phase of this study;
12. Has a prescription dry body weight  $\geq 40$  kg;
13. Continues to meet inclusion criteria 1 through 7.

---

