**A patient will be excluded from the Open-label Extension Phase of the study if any of the additional following criteria are met at the time of entry into the Open-label Extension Phase:**

13. Completed the Double-blind Phase of this study but exhibited adverse events during the course of the Treatment Period that may preclude continued exposure to the study drug;
14. Was noncompliant with protocol procedures during the Double-blind Phase of this study which is indicative of an inability to follow protocol procedures;
15. Has developed a concomitant disease or any medical condition that, in the opinion of the Investigator, could pose undue risk to the patient, impede completion of the study procedures, or would compromise the validity of the study measurements.

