### **8.8 Safety Analysis**

Analysis of all safety data collected during the Double-blind Phase will be performed on the Double-blind Safety Population. The SAP will provide further detail for the analyses to be applied to each safety parameter, and will also include analyses of safety data collected during the Open-label Extension Phase and during exposure to CR845 during both the Double-blind and Open-label Extension Phases. No statistical hypothesis testing will be carried out and no inferential statistical analysis of the safety parameters will be performed.

The baseline value for all analyses of double-blind safety parameters will be defined as the last value obtained prior to the first dose of double-blind study drug and will include both scheduled and repeat (unscheduled) observations.

---

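### The combined CR845 safety summary across both phases counts only patients dosed in the extension, so CR845-arm patients who never enter it are left out

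*Protocol*

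**What the plan says.** Protocol Section 8.5 defines the set by extension dosing: "The Open-label Safety Population is defined as the group of patients who receive at least 1 dose of study drug in the Open-label Extension Phase". It then gives that set two jobs: all safety endpoints collected in the extension, and safety "during exposure to CR845 combining data from both the Double-blind and the Open-label Extension Phases". The synopsis, under Analysis Populations, assigns the same two jobs.

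Two other sections mention the combined analysis. Section 8.1 says the SAP will give details, "including the analysis of safety data during exposure to CR845 across both the Double-blind and the Open-label Extension Phases". Section 8.8 says the SAP will also cover safety data "during exposure to CR845 during both the Double-blind and Open-label Extension Phases". Neither names a different population. The protocol defines no set of all patients who received CR845 in either phase.

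Entry to the extension is filtered as follows:

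- Section 6.2.1, criterion 11: "Has received at least 30 doses of the planned 36 doses of study drug during the Double-blind Phase of this study".
- Section 6.2.2, criterion 13 excludes patients who completed the double-blind phase but "exhibited adverse events during the course of the Treatment Period that may preclude continued exposure to the study drug".
- Section 6.2.2, criterion 14 excludes for noncompliance during the double-blind phase.
- Section 6.2.2, criterion 15 excludes a patient who "Has developed a concomitant disease or any medical condition that, in the opinion of the Investigator, could pose undue risk to the patient".

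All entrants receive CR845, "whether they had been previously administered placebo or CR845" (Section 6.1.2).

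**The concern.** A summary of safety during all CR845 exposure should start at each patient's first CR845 dose and include everyone who had one. Here, a CR845-arm patient's first 12 weeks count only if that patient later enters the extension. Entry depends on survival, on doses received and on how the drug was tolerated, so early exposure is conditioned on a later, tolerability-related event.

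Two things follow. Deaths in the double-blind phase cannot appear in the summary for the CR845 arm. For survivors who enter, the double-blind weeks can still add to an exposure denominator although death was impossible in them. A table presented as CR845 exposure across both phases could be taken to cover all exposed patients when it does not.

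**Working it through.** The point rests on reading the definitions against each other, and the plan states no figure to reproduce.

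**Who is counted**

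| Patient | Double-blind Safety Population | Combined CR845 summary |
|---|---|---|
| CR845 arm, enters extension | yes | yes, both phases |
| CR845 arm, dies in double-blind phase | yes | no |
| CR845 arm, stops and does not enter | yes | no |
| CR845 arm, refused entry (criteria 11, 13 to 15) | yes | no |
| Placebo arm, enters extension | yes, as placebo | yes, extension only |

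The middle three rows are CR845-exposed patients missing from the combined summary.

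**What follows without assumptions**

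- Criterion 11 requires 30/36 = 83.3% of planned doses.
- Double-blind deaths on CR845 in the combined set = 0, because a patient who died cannot receive an extension dose.
- Maximum planned CR845 exposure (Section 6.4.1): former CR845 patients 12 + 52 = 64 weeks; former placebo patients 52 weeks. For the former CR845 group, up to 12/64 = 18.75% of that exposure is time in which death could not be observed.

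**Context from Phase 2 (Sections 4.2.2 and 4.2.3)**, with exact (Clopper-Pearson) 95% intervals for deaths:

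- CR845, all doses: 3/129 = 2.3% (0.5% to 6.6%), where 129 = 44 + 41 + 44.
- CR845 0.5 mcg/kg: 1/44 = 2.3% (0.06% to 12.0%).
- Placebo: 1/45 = 2.2% (0.06% to 11.8%).

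The other two CR845 deaths were at 1.5 mcg/kg, a dose not studied here. All four deaths were judged unrelated to study drug, and their timing is not given. These figures show only that deaths occur in this population over a few weeks. They indicate no excess on CR845 and do not measure the omission.

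**Illustration under assumptions**

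Let f be the share of the CR845 arm that never enters. The protocol does not give f, so 10% to 40% is assumed.

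- Patients omitted = N × f. For N = 175: 17.5 (about 18) to 70. For N = 250: 25 to 100.
- Suppose the overall double-blind SAE risk is R = 21% (the Phase 2 figure, 27/129, all doses, 8 weeks) and non-entrants have RR times the risk of entrants. The proportion seen in entrants alone is q = R / ((1 − f) + f × RR).

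| f | RR = 1 | RR = 2 | RR = 3 |
|---|---|---|---|
| 10% | 21% | 0.21/1.1 = 19.1% | 0.21/1.2 = 17.5% |
| 40% | 21% | 0.21/1.4 = 15.0% | 0.21/1.8 = 11.7% |

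At equal risk nothing moves. The understatement depends entirely on f and RR, and the protocol gives neither.

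**The case against.** The strongest reply is that no data are lost. Section 8.5 sends all double-blind safety endpoints to the Double-blind Safety Population, and Section 8.8.2 summarizes adverse events, serious events, events leading to discontinuation and deaths there by treatment group. Every event of a CR845 non-entrant is shown beside a concurrent placebo arm, which is better evidence on early risk than an uncontrolled pooled table. This stands and is the main limit on the weight of the point. It does not repair the combined summary: CR845-arm entrants appear in both sets of tables, so the two cannot be added to give an all-exposed count. The population sizes tabulated under Section 8.6.1 show how many patients are in each set, not what happened to those left out.

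Second, former placebo patients start CR845 in the extension, and their first weeks on drug are counted in full. This also stands. They have not been selected on CR845 tolerance, so the set does keep an early-exposure cohort. They have, however, survived 12 weeks and passed the same entry criteria, and they cannot stand in for events in the CR845 arm.

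Third, the SAP may add a wider set. That is possible, since the SAP is not at hand. But the population is not an open detail: the protocol names it twice. The rule in Section 8.1 that the SAP prevails is written for analyses of double-blind data, and its reach to the combined analysis is unclear.

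Fourth, the set matches the purpose of the extension in Section 7.1: long-term safety in patients who completed the double-blind period. That is right for extension-only tables. It does not justify the same set once double-blind CR845 exposure is added.

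Finally, Section 6.3.1 lets some patients withdrawn for missed doses enter at discretion. This narrows the gap without closing it.

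**Conclusion.** The point holds. As written, the only analysis described as covering CR845 exposure across both phases excludes CR845-arm patients who never receive an extension dose, and that exclusion is related to survival and tolerability.

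The certain effect is that double-blind deaths on CR845 are fixed at zero in that summary. Understatement of other early events is conditional on non-entrants having more of them; that is plausible given the entry criteria but cannot be sized from the protocol. The consequence is limited to one descriptive, uncontrolled summary. The controlled safety comparison, the efficacy analyses and the type I error are unaffected. The conclusion assumes that the SAP does not already define a set of all CR845-exposed patients. The change is worth making but is not critical to the trial.

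**What to change.** In Section 8.5 and the synopsis, define a further population: every patient who received at least one dose of CR845 in either phase. Assign the combined analysis to it, counting events and exposure from the first CR845 dose, with exposure-adjusted rates. Present it by original arm as well as overall, because former placebo patients begin CR845 already selected by 12-week survival and the entry criteria and have a shorter maximum exposure. Keep the Open-label Safety Population for extension-only summaries. If the SAP already has such a set, align the protocol wording with it.

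The cost is one population definition and some table re-programming. It needs no new data and no change to trial conduct. The sponsor should expect that the combined rates may look less favourable.

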## **8.6 Statistical Summary and Analysis**

### **8.6.1 Patient Disposition**

For the Double-blind Phase, the number of patients enrolled, treated, completed, or discontinued from the study, along with the reason for discontinuation, will be summarized overall and by treatment group.

For all categories of patients (except for the screened patients), percentages will be calculated using the number of enrolled patients as the denominator.

In addition, the number of patients in each analysis population will be tabulated.

### **8.6.2 Protocol Deviations**

Protocol deviations will be identified in several ways: through programmatic checks, through medical reviews, and by clinical research associates during site monitoring. Protocol deviations will be classified as minor or major prior to the database lock. Major protocol deviations will be summarized by treatment group. All protocol deviations will be listed.

### **8.6.3 Demographic and Baseline Characteristics**

Demographic and baseline patient characteristics will be summarized overall and by treatment group and will include age at screening, age category (<45, 45 to >65, 65 to <75, ≥75), gender, ethnicity, race, and prescription dry body weight (kg). Height will not be collected.

Baseline characteristics of the disease will also be summarized overall and by treatment group, and will include variables such as etiology of chronic kidney disease, years since ESRD, duration of pruritus, and time on chronic hemodialysis.

